## **2.20 Section 8.4.1.2 Injection site reactions**

If suspicion of an injection site reaction occurs the subject should be instructed to call the site staff as soon as possible for further guidance.

Possible injection site reactions related both to the bolus and/or basal insulin must be recorded as an AE on an AE form and on a specific injection site reaction form in the eCRF. The following information should be obtained:

- Type of reaction – local or generalised
- Symptoms associated to the event

- Treatment given for the event
- Association with the trial product(s)
- Risk factors associated to the event

The Investigator has to evaluate whether further actions are needed (e.g. extra visits, supervised injection, ~~withdrawal~~*premature discontinuation of trial product*, dermatologist consultation).

## **2.21 Section 8.5.4 eDiary**

At the run-in visit (Visit 2) the subjects will be provided with an eDiary. ~~The eDiary should be returned by the subject at FU1 (Visit 37).~~ The Investigator must carefully instruct the subject in how to use the eDiary. The eDiary is considered as source data for all data entered in the eDiary as described in sections 8.3.2, 8.3.3, ~~and~~ 8.4.1.1 *and* 14.

The Investigator should record the following administrative information in the eDiary web portal:

~~Time and date of next site visit and/or phone contact~~

- Subject ID
- Bolus ~~dosing algorithm~~ titration method to be followed by subject
- Subject randomisation status (mealtime dosing or postmeal dosing)
- *7-9-7-point profile scheduling and confirmation*
- *Visit confirmation*
- *Hypoglycaemic episode confirmation*

All data *entered by the subject in* ~~from~~ the eDiary will be transferred electronically to ~~a~~ *the electronic patient reported outcomes (ePRO) database* ~~trial database~~ from where the Investigator must review all the data for the subjects belonging to the site through the web portal. The review of data must be performed before each visit/phone contact.

The eDiary should be collected by the Investigator at FU1 (Visit 37) and the subject should not be provided with a paper diary for the remaining follow up period. Consequently, source data for FU2 (Phone Contact 38) is the notes written in subject's medical record.

## 2.22 Section 9.3 Storage

**Table 2–1 Table 9.2 Storage of trial products**

Trial product	Storage conditions (not-in-use)	In-use conditions	In-use time a
Faster aspart	Store in refrigerator (2°C – 8°C)  Do not freeze  Protect from light	Store below 30°C  Do not refrigerate  Do not freeze  Protect from light	Use within 4 weeks
Insulin aspart (NovoRapid®)	Store in refrigerator (2°C – 8°C)  Do not freeze  Protect from light	Store below 30°C  Do not refrigerate  Do not freeze  Protect from light	Use within 4 weeks
Insulin degludec	Store in refrigerator (2°C – 8°C)  Do not freeze  Protect from light	Do not store above 30°C  <del>Do not refrigerate</del>  Protect from light  Can be stored in refrigerator (2°C – 8°C)  Do not freeze	Use within 8 weeks

a In-use time starts when first dose is taken.

## **2.23 Section 10 Interactive voice/web response system**

A trial-specific IV/WRS will be set up which can be accessed at any time via the internet or telephone. Access to the IV/WRS must be restricted to and controlled by authorised persons.

IV/WRS is used for:

- Medication arrival
- Screening
- Screening failure
- Run-in dispensing
- Run-in failure
- Randomisation
- Dispensing
- ~~Withdrawal~~ *Treatment discontinuation*
- Completion
- Code break
- Drug accountability
- Data change

As the trial is blinded with regards to faster-acting insulin aspart and NovoRapid® it is important that, at all times during the trial, only DUNs allocated by the IV/WRS are dispensed to the subject.

If a subject requires additional trial product between dispensing visits, the site must perform an additional dispensing session in IV/WRS.

IV/WRS user manuals will be provided to each trial site.

## **2.24 Section 11.2 Breaking of blinded codes**

The IV/WRS will notify Novo Nordisk (monitor and the Global Safety department) immediately after the code is broken.

The code for a particular subject may be broken in a medical emergency if knowing the actual treatment would influence the treatment of the subject. Whenever a code is broken the person breaking the code must print the Code Break Confirmation Notification generated by the IV/WRS, record the reason, and sign and date the document.

When the code is broken, the treatment allocation will be accessible to the Investigator and the Novo Nordisk Global Safety department. If IV/WRS is not accessible at the time of code break the IV/WRS helpdesk should be contacted. Contact details are listed in Attachment I.

If the code has been broken the subject must *discontinue treatment prematurely* ~~be withdrawn from the trial~~ and a “*treatment discontinuation*” ~~withdrawal session~~ must be completed in IV/WRS.

## **2.25 Section 12 Adverse events, and technical complaints and pregnancies**

### **2.25.1 Section 12.1 Definitions**

#### **Adverse event**

An AE is any untoward medical occurrence in a subject administered a product, and which does not necessarily have a causal relationship with this treatment.

An AE can therefore be any unfavourable and unintended sign (including an abnormal laboratory finding), symptom or disease temporally associated with the use of a product, whether or not considered related to the product.

An AE includes:

- A clinically significant worsening of a concomitant illness.
- A clinical laboratory adverse event (CLAE): a clinical laboratory abnormality which is clinically significant, i.e. an abnormality that suggests a disease and/or organ toxicity and is of a severity that requires active management. Active management includes active treatment or further investigations, for example change of medicine dose or more frequent follow-up due to the abnormality.

The following should **not** be reported as AEs:

- Pre-existing conditions, including those found as a result of screening procedures (pre-existing conditions should be reported as medical history or concomitant illness).
- Pre-planned procedures unless the condition for which the procedure was planned has worsened from the first trial related activity after the subject has signed the informed consent.
- Non-serious hypoglycaemia is an AE, but is reported on a hypoglycaemic episode form *in the eDiary* instead of on an AE form, see section 8.4.1.1.

#### **Serious adverse event**

A SAE is an experience that at any dose results in any of the following:

- Death.
- A life-threateninga experience.
- In-patient hospitalisationb or prolongation of existing hospitalisation.
- A persistent or significant disability or incapacityc.
- A congenital anomaly or birth defect.
- Important medical events that may not result in death, be life threateninga or require hospitalisationb may be considered an SAE when - based on appropriate medical judgement - they may jeopardise the subject and may require medical or surgical intervention to prevent one of the outcomes listed in the definition of SAEd.

~~Suspicion of transmission of infectious agents via the trial product must always be considered an SAE.~~

a. The term "life threatening" in the definition of SAE refers to an event in which the subject was at risk of death at the time of the event. It does not refer to an event which hypothetically might have caused death if it was more severe.

b. The term "hospitalisation" is used when a subject:

- Is admitted to a hospital or in-patient, irrespective of the duration of physical stay, or
- Stays at the hospital for treatment or observation for more than 24 hours

Medical judgement must always be exercised, and when in doubt, the hospital contact should be regarded as a hospitalisation. Hospitalisations for administrative, trial related and social purposes do not constitute AEs and should therefore not be reported as AEs or SAEs. Hospital admissions for surgical procedures, planned before trial inclusion, are not considered AEs or SAEs.

c. A substantial disruption of a subject's ability to conduct normal life functions (e.g. following the event or clinical investigation the subject has significant, persistent or permanent change, impairment, damage or disruption in his/her body function or structure, physical activity and/or quality of life).

d. For example intensive treatment in an emergency room or at home of allergic bronchospasm, blood dyscrasiasis or convulsions that do not result in hospitalisation, or development of drug dependency or drug abuse.

*The following events must always be reported as a SAE using the important medical event criteria if no other seriousness criteria are applicable:*

- *Risk of liver injury defined as alanine aminotransferase (ALT) or aspartate aminotransferase (AST) >3 x UNL and total bilirubin >2 x UNL, where no alternative aetiology exists (Hys law)*
- *Suspicion of transmission of infectious agents via the trial product*

## **2.26 Section 12.2 Reporting of adverse events**

All events meeting the definition of an AE must be collected and reported. This includes events from the first trial-related activity after the subject has signed the informed consent until ~~the end of the last phone contact/site visit post treatment follow-up period (Visit 38)~~. The events must be recorded in the applicable eCRF forms in a timely manner, see timelines below and Figure 12-1.

During each contact with the trial site staff, the subject must be asked about AEs and technical complaints, for example by asking: "Have you experienced any problems since the last contact?"

All AEs, either observed by the Investigator or subject, must be reported by the Investigator and evaluated. Novo Nordisk assessment of expectedness is performed according to the following reference documents:

- Faster-acting insulin aspart: Faster-acting insulin aspart IB. Current version and any updates hereof
- NovoRapid®: Company Core Data Sheet. Current version and any updates hereof
- Insulin degludec: *Insulin degludec IB Company Core Data Sheet*. Current version and any updates hereof (Ref. 3)

## **2.27 Section 14 Monitoring procedures**

All data must be verifiable in source documentation other than the eCRF except for *data entered by the subject in the eDiary device and by the investigator through the eDiary web portal. This data will be recorded directly in the device/web portal. All data entered in the eDiary device will be automatically transferred to the ePRO database, where it is kept as a certified copy of the source data. Data entered in the device will upon confirmation of a successful back-up be deleted from the device. Hence the certified copy in the ePRO database is regarded as source data. All data entered through the web portal is entered directly into the ePRO database and hence the ePRO database is regarded as source data.*

Monitors must review the subject's medical records and other source data (eDiary data uploaded/entered into the ePRO trial database and PRO questionnaires) to ensure consistency and/or identify omissions ~~compared to the eCRF~~. If discrepancies are found, the Investigator must be questioned about these.

## **2.28 Section 16 Computerised systems**

Novo Nordisk will capture and process clinical data using computerised systems that are described in Novo Nordisk Standard Operating Procedures and IT architecture documentation. The use and control of these systems are documented.

Investigators working on the trial may use their own electronic systems to capture source data.

The eDiary software and hardware implementation are compliant with the requirements of FDA 21 CFR CFR Part 11 and ICH E6 (EU directive for personal data protection). After trial finalisation, each site will be supplied with long-life DVDs. These DVDs will contain site-specific subject records including the subject's eDiary data and audit trail as well as any data additions and corrections made on each form. The eDiary vendor will furthermore retain and securely store copies of all archived documents and data for 50 years or as required by local data retention laws for trial data.

## 2.29 Section 17 Statistical considerations

If necessary, a statistical analysis plan (SAP) may be written in addition to the protocol, including a more technical and detailed elaboration of the statistical analyses. The SAP will be finalised before database lock.

### General considerations

In general, for endpoints evaluated as a change from baseline and/or where a baseline adjustment is made, baseline is defined as information collected at the randomisation visit (Visit 10). In case a measurement is not available at the randomisation visit, the most recent measurement prior to the randomisation visit will be used as baseline.

*Two observation periods are defined, “in-trial” and “on-treatment”, and it will be specified which period each analysis will use.*

- *In-trial: the observation period from date of randomisation and until last trial-related subject-site contact. The in-trial observation period includes data collected after treatment discontinuation.*
- *On-treatment: the observation period from date of first dose of NovoRapid®/faster-acting insulin aspart and no later than 7 days after the day of last dose of NovoRapid®/faster-acting insulin aspart. The on-treatment observation period includes data collected up to and including 7 days after treatment discontinuation.*

*Analyses of efficacy endpoints will be based on the full analysis set (FAS). All efficacy endpoints will be summarised and analysed using the full analysis set (FAS), unless otherwise stated. Safety endpoints will be summarised using the safety analysis set (SAS) and analysed using the FAS.*

*Presentation of results from a statistical analysis will include the estimated mean treatment effects (LSMeans) for change from baseline, if applicable. Estimated mean treatment differences (or ratios) will be presented together with two-sided 95% confidence intervals for all endpoints analysed statistically.*

*For endpoints measured over time mean values will be plotted to explore the trajectory over time. For survival endpoints, e.g. drop-out pattern, Kaplan-Meier plots are presented for each treatment. Data collected before randomisation will only be summarised descriptively.*

### Estimands

The primary objective, confirming the *efficacy effect* of treatment with mealtime faster-acting insulin aspart *compared to NovoRapid® both in combination with insulin degludec in adults with*

type 1 diabetes, will be assessed comparing by the change from baseline HbA1c to NovoRapid® using a non-inferiority approach.

*More specifically the upper limit of the 95% confidence interval should be compared to a non-inferiority margin of 0.4%. If it is below 0.4% non-inferiority will be considered confirmed and effect demonstrated.*

*The trial also aims to compare treatment arms for a number of confirmatory secondary endpoints. The family-wise type I error rate will be controlled in the strong sense using a hierarchical (fixed sequence) testing procedure. This is based on a priority ordering of the null-hypotheses, and testing them in this order using the two-sided 95% confidence interval approach until an insignificant result appears. The effect is that rejection of the null hypothesis only will be confirmed for analyses where all previous null-hypotheses have been rejected in favour of faster-acting insulin aspart.*

*The steps in the hierarchical testing procedure are:*

**Step 1 (Primary analysis):** HbA1c non-inferiority of meal-time faster-acting insulin aspart versus meal-time NovoRapid®

**Step 2:** HbA1c non-inferiority of post-meal faster-acting insulin aspart versus meal-time NovoRapid®

**Step 3:** 1-hour PPG increments superiority of meal-time faster-acting insulin aspart versus meal-time NovoRapid®

**Step 4:** HbA1c superiority of meal-time faster-acting insulin aspart versus meal-time NovoRapid®

**Step 5:** 1,5-Anhydroglucitol superiority of meal-time faster-acting insulin aspart versus meal-time NovoRapid®

### **Primary Estimand (de facto)**

*The primary estimand is defined as the treatment difference between subjects randomised to faster-acting insulin aspart and NovoRapid® both in combination with insulin degludec, in adults with type 1 diabetes assessed by change from baseline in HbA1c 26 weeks after randomisation for all randomised subjects regardless of treatment discontinuation or use of ancillary therapies. This estimand is a de facto estimand addressing effectiveness.*

*The primary estimand assesses the expected glycaemic benefit a future population with type 1 diabetes can achieve if prescribed to faster-acting insulin aspart as compared to NovoRapid®. By not putting any restrictions on the treatment adherence, this estimand aims at a difference as close as possible to the one that can be expected in real-world clinical practice, provided that the*

*treatment adherence and use of ancillary therapies reflect clinical practice. Thereby the primary estimand provides a treatment difference for clinicians concerning the glycaemic effect of faster-acting insulin aspart compared to NovoRapid® in the day to day life in individual subjects with type 1 diabetes in an adult population.*

### ***Secondary Estimand (de jure)***

*Unlike the primary estimand, a second estimand is defined as the treatment difference in change from baseline in HbA1c 26 weeks after randomisation between faster-acting insulin aspart and NovoRapid® both in combination with insulin degludec in adult subjects with type 1 diabetes if subjects continue on-treatment until 26 weeks. This estimand is a de jure estimand, addressing efficacy.*

*As an alternative to the primary estimand, this estimand provides a more hypothetical treatment difference, but may also be the most sensitive for a non-inferiority comparison, since the intake of ancillary medication may equalize the treatment effect resulting in a difficult assessment if a difference is seen with respect to ancillary medication.*

*The two estimands will be repeated for the endpoints*

- *1-hour PPG increment (meal test)*
- *1,5-Anhydroglucitol*

~~All secondary efficacy endpoints will be summarised and analysed using the FAS. Safety endpoints will be summarised using the safety analysis set (SAS) and analysed using the FAS.~~

~~The impact of protocol deviations and outliers may be investigated further in sensitivity analyses if deemed relevant.~~

~~All continuous endpoints will be summarised descriptively at each visit by treatment. Endpoints that are analysed untransformed, and endpoints that are not formally analysed are summarised by the arithmetic mean, standard deviation (SD), median, and minimum and maximum value. Endpoints that are analysed log transformed are summarised by the geometric mean, coefficient of variation (CV%), median, minimum and maximum value.~~

~~Presentation of results from a statistical analysis will include the estimated mean treatment effects (LSMeans) for change from baseline, if applicable. Estimated mean treatment differences (or ratios) will be presented together with two-sided 95% confidence intervals for all endpoints analysed statistically.~~

~~For endpoints measured over time mean values will be plotted to explore the trajectory over time. For survival endpoints, e.g. drop out pattern, Kaplan Meier plots are presented for each treatment. Data collected before randomisation will only be summarised descriptively.~~

### **2.29.1      Section 17.1 Sample size calculation**

The primary objective of this trial is to confirm *the effect efficacy* of treatment with mealtime faster-acting insulin aspart in combination with insulin degludec. This is done by showing that mealtime faster-acting insulin aspart is non-inferior to mealtime NovoRapid® both in combination with insulin degludec in terms of glucose lowering effect as assessed by mean change from baseline in HbA1c ~~after 26 weeks after randomisation of treatment~~ using a non-inferiority margin of 0.4% (absolute). The non-inferiority margin of 0.4% (absolute) was chosen ~~in accordance with the FDA guidance~~ as described in section 5.2.1. The statistical evaluation will be done as described in section 17.3.

The trial also aims to confirm *efficacy the effect* of treatment with mealtime faster-acting insulin aspart and postmeal faster-acting insulin aspart, for a number of secondary confirmatory endpoints using the hierarchical testing procedure as described in section [2.29.3.1](#) 17.1. The sample size is determined to ensure a sufficient power for the first step (the primary objective: HbA1c non-inferiority of mealtime faster-acting insulin aspart) and the second step (HbA1c non-inferiority of postmeal faster-acting insulin aspart) in the hierarchical testing procedure.

*In, previous trials where faster aspart has been investigated in similar designs, the completion rates have been high. Therefore it will not be unexpected that treatment discontinuation might be as low as 8% where trial discontinuation constitutes half of these.*

Power for the non-inferiority steps are based on a t-statistic under the assumption of a one-sided test of size 2.5%. A zero mean treatment difference for the comparison between mealtime faster-acting insulin aspart and mealtime NovoRapid® is expected, and for the comparison of postmeal faster-acting insulin aspart and mealtime NovoRapid® a mean difference of 0.1% in favor of mealtime NovoRapid® is expected. *As trials in this population where subjects discontinuing treatment are followed up is limited, Based on experience from previous phase 3 trials in subjects with T1DM treated with NovoRapid® a conservative estimate of the SD in change from baseline in HbA1c of 1.42% would be anticipated was chosen.* The power calculation is done using proc power in SAS 9.34. Please refer to Table 17-1 for assumption of the sample size calculation.

Table 2–2 Table 17.1 Specifications assumed for sample size calculation

	Statistical test	Significance level	Analysis population	Non-inferiority margin	SD	Mean difference	Randomisation scheme
Step 1	2-group t-test	One-sided 2.5%	FAS PP	0.4% (absolute)	1.42	0.0	1:1
Step 2	2-group t-test	One-sided 2.5%	FAS PP	0.4% (absolute)	1.42	0.1	1:1

~~As this is a non-inferiority trial, the power calculation is based on the anticipated number of subjects in the PP analysis set. It is assumed that 85% of the randomised subjects will be in the PP analysis set based on previous phase 3 trials in T1DM treated with insulin and sample size is sealed in the FAS to have integer sample size for each arm that adheres exactly to the arm allocation weights (1:1:1).~~

Table 2–3 Table 17.2 Sensitivity of sample size to power in each step

			Primary (Step 1)			Step 2			
N total	N per arm		Mean Diff	SD	Power (step 1) (%)	Mean Diff	SD	Power (step 2) (%)	Power (step 1 and 2) (%)
FAS	FAS	PP							
813	271	<del>230</del>	0	1.42	97.32	0.1	1.42	83.1	<del>80.982.8</del>
999	333	283	0	1.42	99.40	0.1	1.1	89.9	89.189.6
1176	392	<del>333</del>	0	1.42	99.7	0.1	1.42	94.0	<del>93.793.8</del>

From the Table 17.2 it can be seen that, based on the previously defined assumptions, a total of 283333 subjects per arm ~~in the PP analysis set~~ give 99.04% power to conclude HbA1c non-inferiority in the first step. This sample size gives 89.69% marginal power to conclude HbA1c non-inferiority in the second step. ~~Under the assumption of independence between the hypothesis tests, this sample size results in a combined power for the 2 steps of 89.1%, which is considered sufficient.~~

Table 17.3 summarises the anticipated number of subjects in FAS and PP analysis set.

**Table 2.4**      **Table 17.3** Anticipated number of subjects in FAS and PP analysis set

	Mealtime faster-acting insulin aspart	Postmeal faster-acting insulin aspart	Mealtime NovoRapid®	Total
Number of subjects in the FAS	333	333	333	999
Number of subjects in the PP analysis set:	283	283	283	849

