As this is a non-inferiority trial, the power calculation is based on the anticipated number of subjects in the PP analysis set. It is assumed that 85% of the randomised subjects will be in the PP analysis set based on previous phase 3 trials in T1DM treated with insulin and sample size is sealed in the FAS to have integer sample size for each arm that adheres exactly to the arm allocation weights (1:1:1).

Table 17–2 Sensitivity of sample size to power in each step

			Primary (Step 1)			Step 2			Power (step 1 and 2) (%)
N total FAS	N per arm FAS PP		Mean Diff	SD	Power (step 1) (%)	Mean Diff	SD	Power (step 2) (%)	
813	271	230	0	1.1	97.3	0.1	1.1	83.1	80.9
999	333	283	0	1.1	99.1	0.1	1.1	89.9	89.1
1176	392	333	0	1.1	99.7	0.1	1.1	94.0	93.7

From the [Table 17–2](#) it can be seen that, based on the previously defined assumptions, a total of 283 subjects per arm in the PP analysis set give 99.1% power to conclude HbA1c non-inferiority in the first step. This sample size gives 89.9% marginal power to conclude HbA1c non-inferiority in the second step. Under the assumption of independence between the hypothesis tests, this sample size results in a combined power for the 2 steps of 89.1%, which is considered sufficient. [Table 17–3](#) summarises the anticipated number of subjects in FAS and PP analysis set.

Table 17–3 Anticipated number of subjects in FAS and PP analysis set

	Mealtime faster-acting insulin aspart	Postmeal faster-acting insulin aspart	Mealtime NovoRapid®	Total
Number of subjects in the FAS	333	333	333	999
Number of subjects in the PP analysis set:	283	283	283	849

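### Does the amended power table contradict the stated 89.6% power for step 2?

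*Protocol*

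**What the plan says.** Amendment 2, Section 17.1, sizes the trial on the first two steps of the testing hierarchy: "The sample size is determined to ensure a sufficient power for the first step" and for the second, both being HbA1c non-inferiority comparisons with mealtime NovoRapid. The inputs are these:

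- Test: "Power for the non-inferiority steps are based on a t-statistic under the assumption of a one-sided test of size 2.5"%.
- Margin: the comparison is made "using a non-inferiority margin of 0.4% (absolute").
- Step 1: "A zero mean treatment difference for the comparison between mealtime faster-acting insulin aspart and mealtime NovoRapid® is expected".
- Step 2: "a mean difference of 0.1% in favor of mealtime NovoRapid® is expected".

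The original protocol used SD 1.1 and the per-protocol set (230, 283 or 333 per arm). Its Table 17–2 gave step 2 powers of 83.1, 89.9 and 94.0%, and combined powers of 80.9, 89.1 and 93.7%. The sentence below that table said that the chosen size "results in a combined power for the 2 steps of 89.1%, which is considered sufficient".

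Amendment 2 moves to the full analysis set (271, 333 or 392 per arm) and a larger SD. It strikes the paragraph on per-protocol sizing and the combined-power sentence, and it restates step 2 power: "This sample size gives 89.69% marginal power to conclude" non-inferiority. In the amended Table 17.2 the last column is headed "Power (step 1 and 2"). Its cells hold an old and a new figure run together: 80.9 with 82.8, 89.1 with 89.6, and 93.7 with 93.8.

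**The concern.** Read cell by cell, the amended table seems to go wrong in two ways. The step 2 column shows no new figures: it keeps 83.1, 89.9 and 94.0, which belong to SD 1.1 and the per-protocol sizes, and the 333-per-arm row also still shows a step 2 SD of 1.1. The new figures 82.8, 89.6 and 93.8 appear one column further right, under a heading that used to mean combined power for steps 1 and 2. They are not combined powers, and the sentence below the table calls 89.6% marginal.

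If that were the sponsor's final table, the row on which the trial is sized would mix two SDs and two analysis sets. Table and text would disagree on step 2 power (89.9 against 89.6%), and a reader could take 89.6% as the chance of passing both steps. This table is the only place that shows power across sample sizes.

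**Working it through.** **Method.** Two-sample t-test, one-sided 2.5%, n per arm. The standard error is SD × √(2/n), the degrees of freedom are 2n − 2, and the noncentrality is (0.4 − true difference) / SE. Power is the upper tail of the noncentral t beyond the 97.5% point of the central t. The distance to the margin is 0.4 in step 1 and 0.4 − 0.1 = 0.3 in step 2.

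**Original table (SD 1.1, per-protocol sizes).** At n = 283, SE = 1.1 × √(2/283) = 0.0925. The noncentralities are 0.4/0.0925 = 4.33 and 0.3/0.0925 = 3.24, with a critical value of 1.964.

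| n per arm | Step 1 | Step 2 | Product |
|---|---|---|---|
| 230 | 97.33 | 83.11 | 80.89 |
| 283 | 99.08 | 89.95 | 89.12 |
| 333 | 99.68 | 93.99 | 93.69 |

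These agree with the original 97.3/99.1/99.7, 83.1/89.9/94.0 and 80.9/89.1/93.7 to within rounding. The old last column was therefore the product under independence.

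**Which SD does the amendment use?** The text copy reads 1.42, a fusion of the old 1.1 with its replacement. At n = 333, SD 1.42 gives 95.25% and 77.70%, and SD 1.4 gives 95.74% and 78.85%. Neither fits any stated figure. SD 1.2 does.

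**Amended figures (SD 1.2, full analysis set).** At n = 333, SE = 1.2 × √(2/333) = 0.0930. The noncentralities are 4.30 and 3.23, with a critical value of 1.964.

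| n per arm | Step 1 | Step 2 | Product |
|---|---|---|---|
| 271 | 97.21 | 82.77 | 80.46 |
| 333 | 99.02 | 89.64 | 88.76 |
| 392 | 99.65 | 93.77 | 93.45 |

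The new step 1 values (97.2/99.0/99.7) and the new set 82.8/89.6/93.8 both match to the printed decimal. So 82.8/89.6/93.8 are step 2 marginal powers, exactly as the sentence below the table describes 89.6%.

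**Can the table be read as final text?** By its own convention (Amendment 2, Section 1), new text is in italics and deleted text is struck through. In the text copy those marks survive only in part:

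- Old and new digits are fused: SD 1.42 (1.1 to 1.2), step 1 power 97.32 (97.3 to 97.2) and 99.40 (99.1 to 99.0), and 283333 subjects per arm in the text (283 to 333).
- The per-protocol sizes 230 and 333 are marked as deleted, but 283 in the chosen row is not, although the whole calculation moves to the full analysis set.
- One deletion mark covers both 80.9 and 82.8, and another covers both 93.7 and 93.8. Taken literally, the new values would be deleted together with the old ones. In the chosen row the pair 89.1 and 89.6 carries no mark.
- The step 2 SD is amended in the 271 and 392 rows. It reads 1.1 only in the 333 row, where no deletion mark survives.

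The absence of a mark on 83.1/89.9/94.0 is therefore no evidence that these values were kept.

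**The case for a change.** The strongest argument on the other side is the position of the new numbers. Elsewhere in the table, a cell edited in place shows old and new digits fused. The step 2 cells show no such fusion, while the new values turn up in the next column in all three rows. A lost strike-through cannot by itself move an inserted number from one column to another. Nor is this only a comparison with superseded text: Amendment 2 is the operative statement of Section 17.1, and the alleged conflict lies between its own table and its own paragraph.

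The arithmetic behind this stands. The new values are marginal, not joint, and the unmarked step 2 values belong to the old basis. What does not follow is that the sponsor's table is wrong. If the old step 2 figures and the old combined figures were both struck and one new set of step 2 figures was entered in their place, the text copy would look just as it does. That reading also fits the deletion of the combined-power sentence. The alternative, that only the combined column was meant to go and 89.9 stays, implies that 82.8/89.6/93.8 were inserted and deleted in the same amendment, which is implausible. The text copy cannot decide the matter. Should the source PDF show the old step 2 values unstruck beside an unstruck combined-power heading, there would be a clerical slip in one table.

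**Conclusion.** The concern does not hold as an error in the plan. The figure that the plan relies on, 89.6% marginal power for step 2 at 333 per arm, is correct (89.64% at SD 1.2) and is labelled correctly in the text. The apparent conflict rests on old values in a tracked-change table whose deletion marks cannot be trusted.

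The stakes are small even on the worst reading. The step 2 gap at 333 per arm is 89.9 − 89.6 = 0.3 points. Taken as joint power, 89.6% would be 89.6 − 88.8 = 0.8 points too high under independence. Allowing for the shared comparator arm, joint power is 89.2 to 89.3%, a difference of 0.3 to 0.4 points. At 271 per arm, a size that was not chosen, the independence gap is larger: 82.8 − 80.5 = 2.3 points. The 333 per arm, the 999 in total, the margin and the order of testing are unaffected.

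This rests on one assumption, that the fused 1.42 stands for SD 1.2. The document does not print that value cleanly, but of the SDs tried only 1.2 reproduces the amended powers. Which table entries were struck remains unknown without the source PDF or a consolidated protocol.
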